and is currently undergoing study as a potential treatment of Norovirus (ClinicalTrials.gov Identifier: NCT02371538). Systemic administration of immunoglobulin has provided conflicting evidence of clinical impact on Norovirus infection.^(1, 3) A novel monoclonal Norwalk-virus specific antibody has been developed and found to be effective in a chimpanzee model of infection, but efficacy in humans remains unproven.⁽⁵⁸⁾ A number of drugs that are currently approved, including nitazoxanide, ribavirin, suramin and human interferon- α have activity against Norovirus (Table 2). Several drugs including favipiravir in early phase of development show promise in the treatment of Norovirus (Table 2).^(1, 3, 36)

Nitazoxanide (2-acetyloxy-*N*-(5-nitro-2-thiazolyl) benzamide Alinia[®]) is a thiazolide compound that is rapidly hydrolyzed to its active metabolite, tizoxanide, which has broad activity against bacteria, parasites and viruses.⁽⁵⁹⁾ Nitazoxanide is approved by the United States Food and Drug Administration as an oral suspension (age \geq 1 year) and a 500 mg tablet (age \geq 12 years) for treating diarrhea caused by *Giardia lamblia* and *Cryptosporidium parvum*. The nitazoxanide table contains 500 mg of nitazoxanide and the following inactive ingredients: maize starch, pregelatinized corn starch, hydroxypropyl methylcellulose, sucrose, sodium starch glycolate, talc, magnesium stearate, soy lecithin, polyvinyl alcohol, xanthan gum, titanium dioxide, FD&C Yellow No. 10 Aluminum Lake, FD&C Yellow No. 6 Aluminum Lake, and FD&C Blue No. 2 Aluminum Lake.

Pharmacology of Nitazoxanide

[figure not shown]
After oral administration, maximum plasma concentrations of the active metabolites tizoxanide and tizoxanide glucuronide are observed within 1-4 hours. The active metabolite elimination half-life is 7.3 hours. The parent nitazoxanide is not detected in plasma. Key pharmacokinetic parameters are summarized in Table 3. From this data, it is clear that the oral suspension is not bioequivalent to the tablet formulation. The relative bioavailability of the suspension compared to the tablet is 70%.

Table 3: Plasma Pharmacokinetic Values Following a Single Oral Dose of Nitazoxanide

¹Mean (\pm SD). ²Mean (Range)

Formulation	Dose	Age (Yrs)	Tizoxanide			Tizoxanide Glucuronide		
			C _{max} ¹ (μ g/mL)	T _{max} ² (Hr)	AUC ¹ (μ g•hr/mL)	C _{max} ¹ (μ g/mL)	T _{max} ² (Hr)	AUC ¹ (μ g•hr/mL)
Tablet	500mg	12-17	9.1 (6.1)	4.0 (1-4)	39.5 (24.2)	7.3 (1.9)	4.0 (2-8)	46.5 (18.2)

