4. Stool for Pathogen Screen: This assay will be performed in the Diagnostic Infectious Diseases Testing Laboratory (Cincinnati Children's Hospital Medical Center (CCHMC, Cincinnati, OH) which will be provided a 1-gram aliquot of stool from the [name] Laboratory. Day 1 stool specimen and non-formed stool samples from subsequent visits will be screened for additional pathogens (Bacteria- *Campylobacter* (jejuni, coli and upsaliensis), *Clostridium difficile* (Toxin A/B), *Plesiomonas shigelloides*, *Salmonella* species, *Yersinia enterocolitica*, *Vibrio* species (parahaemolyticus, vulnificus and cholerae), Diarrheagenic *E.coli*/*Shigella* including, Enteroaggregative *E. coli* (EAEC), Enteropathogenic *E. coli* (EPEC), Enterotoxigenic *E. coli* (ETEC), Shiga-like toxin-producing *E. coli* (STEC), *Shigella*/Enteroinvasive *E. coli* (EIEC); Parasites- *Cryptosporidium*, *Cyclospora cayetanensis*, *Entamoeba histolytica*, *Giardia lamblia*; Viruses - Adenovirus F40/41, Astrovirus, Norovirus GI/GII, Rotavirus A, Sapovirus (I, II, IV and V)) using the FDA-cleared FilmArray system from BioFire Diagnostics (bioMerieux, Marcy l'Etoile, France). After collection in the stool hat, the subjects can wipe down and disinfect the outside of the container and place it in a bag for transport then refrigerate until they come to their visit with the research staff. The sample must have been produced within 24 hours of the visit and if it exceeds 24 hours it must be disposed. Subject would be encouraged to provide another sample within the visit window and if not, a rectal swab may be used for virus detection.

Table 5: Protocol PRO Completion Guide

Phase	Treatment					Post-treatment monitoring							Unscheduled Visit	Early Termination Visit
	Screen Enroll Day 1	Day 7 (±3 d)	Day 14* (±3 d)	Day 21* (±3d)	Day 28 (+3 d)	Day 35 (±3d)	*Day 53 (±7d)	*Day 60 (±14 d)	*Day 113 ±7d	*Day 120 (±14 d)	*Day 173 ±7d	Day 180 (±14 d)		
Daily Diary		Days 1-7	Days 8-14	Days 15-21	Days 22-28			Days 29-60		Days 61-120		Days 121-180	X	Last week before term
Weekly Recall/ Phone Packet	X	X	X	X	X	X	X	X	X	X	X	X	X	X
Detailed PROs Packet	X				X			X		X		X		X

Daily Diary: To be completed by subject daily. Diary 1-28 days; Diary 29-180 days See MOP for details.

Weekly Recall Packet: To be completed by study staff. See MOP for details.

Detailed PROs Packet: To be completed by study staff. This will include PROMIS and QOL Questionnaires. See MOP for details.

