there are statistically significant pairwise contrasts between the groups on unadjusted change between baseline and subsequent time points, and on adjusted change (controlling for baseline).

For exploratory outcome 14, a Cox proportional hazards model will be utilized to determine the effect of the presence or absence of co-pathogens at any time point on the time to clinical resolution of Norovirus symptoms for at least 48 hours through Day 180. A binary covariate representing the presence or absence of co-pathogens will be included in the model. As an alternative, if it is determined that subjects' co-pathogen status changes often throughout the study, the effect may be considered as a time-varying covariate.

For exploratory outcome 15,16-please see section 11.4.3.3

Virologic Improvement:

For exploratory outcomes 17-19, analysis of Norovirus sequencing data, mutations will be compared between the nitazoxanide and placebo treatment groups. Non-synonymous/synonymous (dN/dS) mutation analysis will be performed for each subject to determine whether selection is occurring within the polymerase, as well as Viral Epidemiology Signature Pattern Analysis (VESPA) and Random Effects Likelihood and Fixed Effects Likelihood (REL and FEL) methods to perform site-specific analyses and to identify trends within the nitazoxanide treatment group and differences between the treatment and placebo groups.

For exploratory outcome 20, a Cox proportional hazards model will be utilized to determine the effect of the presence or absence of co-pathogens at any time point on the time to first negative viral load through 180 days. A binary covariate representing the presence or absence of co-pathogens will be included in the model. As an alternative, if it is determined that subjects' co-pathogen status changes often throughout the study, the effect may be considered as a time-varying covariate.

For exploratory outcome 21, please see section 11.4.3.3

Immunologic Response:

For stool immunoglobulin testing, Day 1 will assess baseline values, Day 28 will assess end of treatment levels and Day 60 will give a single post-treatment level. The proportion of subjects with ≥ 4 -fold rise in Norovirus-specific Ig titers from Day 1 will be assessed at each follow-up time point comparing the nitazoxanide treatment group to the placebo group.

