Number of Type 6 or 7 Stools:

The number of Type 6 or 7 stools through Day 28 will be defined as the sum of the responses to the quantitative Daily Diary Diarrhea Questions during the Treatment Phase (see above). Missing responses will be left as missing.

Number of Days of IV Hydration or Total Parenteral Nutrition (TPN) Therapy:

The number of days of IV hydration or TPN therapy will be defined as the number of days with a concomitant medication with any indication related to IV hydration or TPN therapy. A blinded review of the concomitant medication data will be performed by the Medical Monitor to identify medications that should be included in the analysis. Days prior to Day 1 will not be included in the calculation of the number of days. Medications that are ongoing after Day 28 will be censored at 28 days.

Co-pathogen Status:

Co-pathogen status will be determined by the BioFire stool pathogen screen on Days 1 and 180. Co-pathogen status will be determined on Days 7, 14, 21, 28, 60, 120, and with recurrent diarrhea if unformed stool is present on study day. Analyses will only include whether pathogens were detected or not and will not differentiate by co-pathogen type. The listing will include which co-pathogens were detected at each subject/visit ([Listing 18](#)).

Secretor Status:

Saliva is collected at screening to determine H type 1 secretor status (phenotyping), while a buccal swab is collected to perform FUT2 genotyping. Phenotype and genotype results will either be “secretor” or “non-secretor” for each subject.

Norovirus-Specific Immunoglobulins (Ig):

Results below the lower limit of detection (LLOD) will be imputed as $\frac{1}{2}$ the LLOD. Results above the upper limit of detection (ULOD) will be imputed as the ULOD.

Responders:

A subject is classified as a responder if he or she has a four-fold or greater increase in Norovirus-specific Ig titers compared to baseline (Day 1).

Study Day:

Study day will be reported as the number of days from randomization with the day of randomization reported as study day 1.

Days Post-Randomization:

Days post-randomization will be reported as the number of days since randomization; if an event began on the day of randomization, the days post-randomization is reported as 0.

Duration:

Duration will be reported as the difference between the start and end dates, inclusive of the day the event started.

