Additional exploratory efficacy variables include chromaturia and co-pathogens. Chromaturia (discoloration of urine) will be based on unsolicited self-reporting. Co-pathogen status in stool will be determined utilizing the BioFire FilmArray Gastrointestinal Panel to screen for a range of pathogens (*Campylobacter* (*C. jejuni/C. coli/C. upsaliensis*)), *Clostridium difficile* (*C. difficile*) toxin A/B, *Plesiomonas shigelloides*, *Salmonella*, *Vibrio* (*V. parahaemolyticus/V. vulnificus/V. cholerae*), including specific identification of *Vibrio cholerae*, *Yersinia enterocolitica*, Enterotoaggregative *Escherichia coli* (EAEC), Enteropathogenic *Escherichia coli* (EPEC), Enterotoxigenic *Escherichia coli* (ETEC) *lt/st*, Shiga-like toxin-producing *Escherichia coli* (STEC) *stx1/stx2* (including specific identification of the *E. coli* O157 serogroup within STEC), *Shigella/Enteroinvasive Escherichia coli* (EIEC), *Cryptosporidium*, *Cyclospora cayetanensis*, *Entamoeba histolytica*, *Giardia lamblia* (also known as *G. intestinalis* and *G. duodenalis*), Adenovirus F 40/41, Astrovirus, Norovirus GI/GII, Rotavirus A, Sapovirus (Genogroups I, II, IV, and V)). Pathogen screening will occur on Days 1 and 180 for all subjects along with Days 7, 14, 21, 28, 60, 120, and with recurrent diarrhea if unformed stool on study day.

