The effect of co-pathogens, as determined by the BioFire stool pathogen screen, on the primary outcome measure is presented in [Table 34](#), where the presence or absence of co-pathogens will be represented as a binary covariate in the Cox proportional hazards model. If it is determined that subjects' co-pathogen status changes often throughout the study, the effect of co-pathogens will be a time-varying covariate instead of a binary covariate.

Time from randomization until clinical resolution of Norovirus symptoms for at least 48 hours through Day 180. Clinical resolution will be assessed from the daily diary by the subject and will be defined as cessation of vomiting and no stools classified by the Bristol Stool Chart as diarrhea (Type 6 or 7) from the total population compared to the subgroup of subjects who do not report chromaturia (discoloration of urine) based on unsolicited self-reporting is presented in [Table 18](#).

The effect of co-pathogens, as determined by the BioFire stool pathogen screen, on the time from randomization to first negative viral load through 180 days is presented in [Table 35](#) and [Table 36](#) for Norovirus GII and Norovirus GI test types, respectively, where the presence or absence of co-pathogens will be represented as a binary covariate in the Cox proportional hazards model. If it is determined that subjects' co-pathogen status changes often throughout the study, the effect of co-pathogens will be a time-varying covariate instead of a binary covariate.

Time from the randomization to first negative viral load through 180 days and the change in viral titer between Day 1 and 180 from the total population compared to the subgroup of subjects who do not report chromaturia (discoloration of urine) based on unsolicited self-reporting will be presented in [Table 23](#) and [Table 24](#) for Norovirus GII and Norovirus GI test types, respectively .

Analyses of the following exploratory outcome measures are not covered in this SAP:

- Time to ≥ 1 log reduction in stool Norovirus genome copies
- Change in quantitative Norovirus load in the stool between Day 1 and Day 7, 14, 21, 28, 60, 120, and 180.
- Change in Norovirus sequence from Day 1 to Days 28 and 60.

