Listing 16: 16.2.6.5: Individual PROMIS Scores Data – Physical Function, Emotional, and Gastrointestinal Symptoms

[Implementation Note: Listing will provide the PROMIS T-scores for Physical Function, Depression, Anxiety, Fatigue, and GI Symptoms.]

Treatment Group	Subject ID	Transplant Type	Duration of Symptoms	Planned Time Point	Actual Study Day	Physical Function	Depression	Anxiety	Fatigue	GI: Diarrhea	GI: Nausea	GI: Fecal Incontinence	GI: Belly Pain

Listing 17: 16.2.6.4: Individual NoV PCR Results Data

[Implementation Note: “N/A” will be listed in the NoV GI PCR Test Result column if NoV GI test not conducted.]

[Implementation Note: Update as appropriate for your study assay/strain and endpoints. In the CSR, Subject ID should be USUBJID (not PATID) for purposes of de-identification.] Listing should be sorted by Treatment Group, Subject ID, Planned Time Point.]

Treatment Group	Subject ID	Transplant Type	Duration of Symptoms	Planned Time Point	Actual Study Day	NoV GII PCR Test Result	NoV GI PCR Test Result

Listing 18: 16.2.6.7: Individual Co-pathogen Status Data

[Implementation Note: Update as appropriate for your study assay/strain and endpoints. In the CSR, Subject ID should be USUBJID (not PATID) for purposes of de-identification.] Listing should be sorted by Treatment Group, Subject ID, Planned Time Point.]

Treatment Group	Subject ID	Transplant Type	Duration of Symptoms	Planned Time Point	Actual Study Day	Co-Pathogen Detected
						[e.g. Norovirus GI/GII, Norovirus GI/GII/Clostridium difficile toxin A/B, None]

Listing 19: 16.2.6.8: Individual Baseline Secretor Status Data

[Implementation Note: Update as appropriate for your study assay/strain and endpoints. In the CSR, Subject ID should be USUBJID (not PATID) for purposes of de-identification.] Listing should be sorted by Treatment Group, Subject ID, Planned Time Point.]

Treatment Group	Subject ID	Transplant Type	Duration of Symptoms	Phenotype Result	Genotype Result
				Secretor/Non-secretor	Secretor/Non-secretor

Listing 20: 16.2.6.9: Individual Serum Immunology Response Data

[Implementation Note: In the CSR, Subject ID should be USUBJID (not PATID) for purposes of de-identification.] Listing should be sorted by Treatment Group, Subject ID, Planned Time Point.]

Treatment Group	Subject ID	Transplant Type	Duration of Symptoms	Planned Time Point	Actual Study Day	NoV IgA Result	NoV IgG Result	Total IgG Result	NoV IgM Result

Listing 21: 16.2.6.10: Individual Stool Immunology Response Data

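### Co-pathogen status is defined as any detection on a panel that includes norovirus itself, so a norovirus-only stool counts as co-pathogen present

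*SAP*

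**What the plan says.** - **Definition.** SAP 3.3 (Co-pathogen Status) takes the status from the BioFire stool screen and reduces it to yes or no: "Analyses will only include whether pathogens were detected or not and will not differentiate by co-pathogen type". Organism-level results go to a listing: "The listing will include which co-pathogens were detected at each subject/visit".
- **Panel.** SAP 4.5.1 lists the targets used to determine co-pathogen status. The viral ones are "Adenovirus F 40/41, Astrovirus, Norovirus GI/GII, Rotavirus A, Sapovirus (Genogroups I, II, IV, and V". Protocol 8.2.1 and 8.2.2 also name Norovirus GI/GII.
- **Worked example.** In SAP Appendix 3, the Co-Pathogen Detected column of Listing 18 carries the sample entries "e.g. Norovirus GI/GII, Norovirus GI/GII/Clostridium difficile toxin A/B, None".
- **Use.** SAP 8.3 analyses the effect on time to clinical resolution (outcome 14, Table 34) and on time to first negative viral load (outcome 20, Tables 35 and 36), "where the presence or absence of co-pathogens will be represented as a binary covariate in the Cox proportional hazards model". If status changes often, the covariate becomes time-varying instead.
- **Time basis.** For outcome 14, Protocol 11.4.5 refers to the "effect of the presence or absence of co-pathogens at any time point on the time to clinical resolution of Norovirus symptoms". SAP 8.3 does not say which visit or visits set the binary flag.
- **Small groups.** SAP 8 drops subgroups with fewer than five subjects per arm from efficacy tables and figures.

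**The concern.** A co-pathogen analysis in a norovirus trial should compare subjects who carry norovirus plus another organism with subjects who carry norovirus alone. The rule as written puts both groups in the present category. The absent category is then left with stools in which nothing was detected, norovirus included. A programmer who follows SAP 3.3 and checks the result against the Listing 18 example would code it that way.

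The co-pathogen rows of Tables 34 to 36, and the covariate in the underlying Cox models, would then be labelled as co-infection while largely recording whether norovirus was found on the panel.

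**Working it through.** The plan gives no co-pathogen prevalence and no BioFire detection rate, so there is no figure to reproduce. The check has four parts.

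**1. What the text settles.** SAP 3.3 says any pathogen, SAP 4.5.1 puts norovirus among the pathogens, and neither document takes it out. Listing 18 shows norovirus alone as a value distinct from None. Against this, the word co-pathogen, and the statement in Protocol 8.2.1 that stools "will be screened for additional pathogens", point to organisms other than norovirus. The intent is fairly clear, but the operational rule does not implement it.

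**2. Outcome 14 under the literal flag, Day 1 only.** Inputs: 31 subjects enrolled (SAP 6.6). Assumed: arms of 16 and 15; a share *s* with norovirus detected by BioFire on Day 1; a share *q* with another target detected; *s* and *q* independent. Then

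P(absent) = (1 − s)(1 − q), and expected absent = 31 × (1 − s)(1 − q).

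The chance that the absent row keeps at least five in each arm is the product of two binomial tails, P(X ≥ 5) for n = 16 and for n = 15.

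| s | q | P(absent) | Expected absent of 31 | Chance row is kept |
|---|---|---|---|---|
| 0.98 | 0.4 | 0.02 × 0.6 = 0.012 | 0.4 | under 0.01% |
| 0.90 | 0.1 | 0.10 × 0.9 = 0.09 | 2.8 | about 0.01% |
| 0.80 | 0.4 | 0.20 × 0.6 = 0.12 | 3.7 | 0.1% |
| 0.80 | 0.1 | 0.20 × 0.9 = 0.18 | 5.6 | 2% |
| 0.50 | 0.4 | 0.50 × 0.6 = 0.30 | 9.3 | 27% |
| 0.50 | 0.1 | 0.50 × 0.9 = 0.45 | 13.95 | 80% |

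An any-time flag, as in Protocol 11.4.5, can only raise the present share. The row count depends on *s*. The meaning of absent does not: in every line of the table it is no norovirus and nothing else.

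**3. Outcome 20 under the literal flag.** SAP 3.3 (Viral Load) excludes subjects who were not positive for GII or GI at baseline. Everyone analysed therefore has norovirus in the baseline stool by the central quantitative assay. BioFire is a different assay, so *s* = 1 is not guaranteed, but it should be close to 1. The time-varying fallback does not help: unless another organism is present, the flag switches from present to absent when norovirus disappears, which is in substance the endpoint. The trigger for using that fallback, frequent change of status, would itself be driven by clearance.

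**4. After norovirus is removed from the flag.** P(present) = q, with the same assumed arms:

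| q | Expected present of 31 | Present row kept | Both rows kept |
|---|---|---|---|
| 0.10 | 3.1 | under 0.1% | under 0.1% |
| 0.20 | 6.2 | 3% | 3% |
| 0.30 | 9.3 | 27% | 27% |
| 0.40 | 12.4 | 65% | 64% |

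The corrected flag measures the right thing but may still be too sparse to tabulate.

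**The case against.** The strongest reply is that nobody would count norovirus as a co-pathogen in a norovirus trial. The variable's name and the protocol's stated purpose for the screen say otherwise, and the contrary evidence is an example in a listing shell whose implementation note tells the programmer to adapt it. A listing can print raw panel output without defining a derived variable. This is fair as to intent. It does not supply the missing exclusion, and the only worked example points the other way.

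Several stronger readings are tempting, and the documents do not support them:

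- *Nearly every subject will be classed as co-infected.* For outcome 14 this needs both the literal reading and a high detection rate. Entry requires only a local positive test within 14 days, and the SAP itself provides for subjects negative at baseline.
- *Outcomes 14 and 20 cannot be answered.* Organism-level results are kept in Listing 18, so a norovirus-free flag can be derived at any time.
- *Tables 34 to 36 would report the effect of norovirus detection.* The shells show nitazoxanide-to-placebo hazard ratios within co-pathogen rows and overall. They have no hazard ratio for the flag, and the five-per-arm rule removes table rows, not the model covariate.
- *Pooling Giardia and Cryptosporidium with other organisms is an error.* Protocol 2.1 says nitazoxanide is approved for diarrhea caused by these two. However, exclusion 1 in Protocol 5.2 bars other identified infectious causes, with exceptions only where the PI documents that the finding is not clinically significant. The documents do not show that any such subject was enrolled. Pooling is a stated choice and defensible with 31 subjects.

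**Conclusion.** The point holds as a defect in a derived variable. The stated rule, the panel and the listing example together make a norovirus-only stool co-pathogen present, and no text prevents this. The effect is firmest for outcome 20, where present on Day 1 would be nearly universal; this rests on BioFire agreeing closely with the baseline quantitative PCR. For outcome 14 the imbalance ranges from almost no absent subjects (0.4 to 2.8 of 31 at 90-98% detection) to 9 to 14 at 50%. Those figures rest on assumed detection rates, an assumed *q* of 0.1 to 0.4, and independence. That absent is the wrong comparator rests only on the literal rule.

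Both outcomes are exploratory, and SAP 14.2 expects the analyses to be mainly descriptive, so the primary conclusion is not affected. The definition should still be corrected before the tables are programmed.

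**What to change.** 1. In SAP 3.3, define co-pathogen present as at least one BioFire target other than Norovirus GI/GII.
2. State there whether the flag is baseline, any-time or time-varying. Between Day 1 and Day 180 the screen is run only on unformed stool, so a flag built on later visits depends on continuing symptoms.
3. Change the Listing 18 example so that norovirus alone is not shown as a co-pathogen.
4. State in the CSR how many subjects fall in each row and, if the present row is below five per arm, that sample size rather than the definition prevents the contrast.

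Separate flags for Giardia and Cryptosporidium are optional.

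The cost is a few SAP sentences and one derived variable. Target-level results are already planned for Listing 18, so no new data are needed.
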